8.2 Data Analysis Plan

Efficacy analysis for primary outcome

Because of the within subject correlation for the primary outcome (% fertile female worms), we will use a generalized linear mixed model approach (PROC GLIMMIX, SAS)⁴⁶. Generalized linear mixed models (GLMM) permit modeling of non-normal outcomes while accounting for correlation among observations within a group. In the present study, the primary outcome is binary (0=non-fertile female worm, 1=fertile female worm) and worms within a person are not independent. To model these data we will use a GLMM assuming a binomial distribution with a logit link function,

and person will be treated as a random effect. Further, while we do not anticipate an effect of village on our outcomes, if subjects within village are correlated the GLMM can be extended to account for this correlation. A two-sided P -value ≤ 0.05 is considered significant for these analyses.

Efficacy analysis for secondary outcomes

Similar to the analysis of the primary outcome, percentage of all adult worms that are viable will be analyzed using a GLMM. Percent of persons with zero MF at 18 months will be analyzed using a generalized linear model assuming a binomial distribution and a logit link function. The difference between pre and post treatment MF counts (% reduction) will be analyzed using a paired t-test and will be transformed as necessary to meet the assumptions of this analysis. A P -value of 0.05 will be considered significant for all secondary outcomes.

Safety

The primary safety analysis will focus on AEs with severity grade 3 or greater. Secondary analyses will separately consider all AEs and ocular AEs. AEs will be assessed daily for 7 days after treatment and 3 months after treatment. This will include general assessments and detailed ophthalmological examinations on day 7 and 3 months after treatment. AE rates and severity will be compared across the three treatment groups using logistic regression analysis; with Student's t -test will be used to assess differences for individual AEs. The data will also be examined using a generalized linear mixed model that as described below can model non-normal outcomes and examine correlations among the different events and how these change over time. In this model, we can also examine the impact of baseline Mf burdens prior to treatment and other potential risk factors (age, sex, location, etc.) on AEs.

Note that the samples sizes per treatment group in this study are not sufficient to provide a robust safety profile (e.g., high confidence that the rate of SAEs after treatment is less than 0.1%). This proof of concept study will allow for initial safety assessments to be performed. Additional, larger studies will be required to establish a more complete safety profile. The safety assessments put in place for this study along with the frequent and ongoing review by the DSMB will provide a strong foundation to evaluate the participant's safety throughout the study.

Data from all participants in this study will be analyzed for safety and efficacy outcomes. The study population for the primary and secondary endpoints related to adult worm viability and fertility are persons who were enrolled and who have nodulectomies performed 18 months after treatment. The study population for secondary efficacy outcomes related to microfilariae in the skin are participants who were enrolled in the study who have follow-up microfilaria testing by skin snip examination at time points (12, 18 months) as indicated in the diagram on page 26 of the protocol. The study population for the early (7 day) safety analysis are participants who receive the study drugs who have safety assessments during the 7 days after dosing. A separate safety analysis will consider data from the follow-up examinations conducted 3 months after dosing.

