8 STATISTICAL CONSIDERATIONS

8.1 Sample Size Determination (Power calculation)

The *primary outcome* variable used for our power analysis is the % fertile female worms (100 x fertile female worms/ total female worms) for each of the three drug treatments: (1) single-dose IVM (IVM alone); (2) single dose of IVM + DEC and albendazole (IDA1); (3) three daily doses of IVM + DEC and albendazole (IDA3). Power calculations for our primary treatment-group comparison (IVM /ALB vs IDA1) assumed that 30% of the total worms will be fertile females in IVM/ALB group and that 15% of the total worms will be fertile females in the IDA1 group. For our secondary treatment-group comparison (IVM/ALB vs IDA3), we assumed that 10% of the total worms were fertile females for the IDA3 group. On average, we assumed that there will be 6 total female worms to evaluate in 3 nodules per person after treatment. In our analysis we treated each worm within a subject as a Bernoulli trial (0=non-fertile female worm, 1=fertile female worm), and we used an intra-class correlation (ICC) of 30% to account for within subject correlation among the trials. The ICC and cluster size (# female worms/person) adjusts the sample-size estimate using the following formula: $1 + \text{ICC} \times (\text{Cluster size} - 1)$ ^{44, 45}. To achieve 80% power at a two-sided alpha-level of 0.05, we will need nodule histology data from 51 subjects in each treatment group for the primary treatment-group comparison (IVM/ALB vs IDA1). The expected % difference for our secondary treatment-group comparison (IVM/ALB vs IDA3) powered at 80% and an alpha of 0.05, would require 26 subjects/group. After accounting for a 20% drop-out rate, a sample size of at least 61 subjects per treatment group will enable us to address both the primary (IVM/ALB vs IDA1) and secondary (IVM/ALB vs IDA3) treatment-group comparisons. Furthermore, we will attempt to enroll additional subjects beyond the target of 61 to provide some protection against other (unforeseen) factors that could decrease the power of this study (e.g., within village correlation, smaller effect size, higher drop-out rate than anticipated). The study will provide preliminary safety data, but a much larger study will be required to provide a precise safety comparison of IVM/ALB vs IDA.

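### Section 8.2 gives no estimation method for the primary mixed model; under pseudo-likelihood the person-specific log odds ratio would be shrunk by about 14–20%, with the test essentially unaffected

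*Combined protocol and SAP*

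**What the plan says.** Section 8.2 (efficacy analysis for the primary outcome) treats each female worm as one observation: "the primary outcome is binary (0=non-fertile female worm, 1=fertile female worm"). The model is specified in three parts: the software ("we will use a generalized linear mixed model approach (PROC GLIMMIX, SAS"), the distribution and link ("To model these data we will use a GLMM assuming a binomial distribution with a logit link function"), and the clustering ("and person will be treated as a random effect"). A village effect may be added. The decision rule is "A two-sided P -value ≤ 0.05 is considered significant for these analyses". Worm viability, a secondary endpoint, is to be analysed in the same way.

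Section 8.1 gives the design values. It "assumed that 30% of the total worms will be fertile females in IVM/ALB group", against 15% with one IDA dose and 10% with three. It assumes an average of 6 female worms per person, and for clustering "we used an intra-class correlation (ICC) of 30% to account for within subject correlation among the trials". The scale of that ICC is not stated. The result is 51 persons per group with nodule histology.

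Neither section names an estimation technique (pseudo-likelihood, Laplace or quadrature), and neither says which effect measure will be reported from the model.

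**The concern.** Several techniques can fit the model in Section 8.2, and they do not give the same answer for this kind of data. Linearised pseudo-likelihood is known to be biased when the outcome is binary, the clusters are small and the between-person variance is sizeable. All three hold under Section 8.1. Two analysts who follow Section 8.2 exactly could therefore report noticeably different odds ratios from the same worms.

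At stake are the size of the treatment effect on the primary endpoint, its confidence interval and the person variance. Section 4 states the primary efficacy objective as a comparison of the effects of three regimens, so the size of the effect is a result in its own right. A later trial may also take its person variance from this one.

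**Working it through.** **Inputs from Section 8.1.** 30% versus 15% fertile (10% for three IDA doses), 6 worms per person, ICC 0.30, 51 per group, two-sided alpha 0.05, 80% power.

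**Reproducing the plan's figure.** The two-proportion formula with pooled variance under the null gives 121 worms per arm for 30% versus 15%. The design effect is 1 + 0.30 × (6 − 1) = 2.5. Then 121 × 2.5 / 6 = 50.4, so 51 persons. For 30% versus 10%: 62 × 2.5 / 6 = 25.8, so 26. Both agree with the plan.

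**Assumptions not in the documents.** The software default is pseudo-likelihood. The person effect is normal with the same variance in each arm. The ICC scale is unstated, so both readings were used:

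- Latent scale: variance = 0.30/0.70 × π²/3 = 1.41, SD 1.19.
- Observed scale at 30% fertile: variance 2.63, SD 1.62.

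**True effect.** The planned 30% and 15% are averages over persons, with an odds ratio of (0.15/0.85)/(0.30/0.70) = 0.41. The logit model estimates the person-specific odds ratio. Choosing intercepts so that the averages are 30% and 15% gives a log odds ratio of −1.08 (OR 0.34) for the latent reading and −1.23 (OR 0.29) for the observed reading.

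**Simulation, 51 per arm.** Each trial was fitted by residual pseudo-likelihood (PL) and by Gauss–Hermite maximum likelihood (ML). The latent row uses cluster sizes varying around a mean of 6, and the observed row uses 6 worms each.

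| ICC 0.30 reading | True log OR | PL mean (SD; mean SE) | ML mean (SD) | Median PL variance |
|---|---|---|---|---|
| Latent | −1.082 | −0.954 (0.301; 0.307) | −1.097 (0.349) | 0.93 |
| Observed | −1.225 | −0.985 (0.343; 0.338) | −1.230 (0.436) | 1.51 |

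- *Shrinkage.* With 6 worms for everyone, PL recovers 0.85–0.86 of the true log OR (latent) and 0.79–0.80 (observed). ML recovers 0.99–1.00 in both. With varying cluster sizes the latent ratio is 0.954/1.082 = 0.88. With 2,000 persons per arm the PL ratios are 0.86 and 0.79, so a larger sample does not remove the bias.
- *Smaller ICC.* The shrinkage is about 8% at an observed-scale ICC of 0.10 and 14% at 0.20.
- *Person SD.* √0.93/1.187 = 0.81 and √1.51/1.621 = 0.76, so it is 19% and 24% too small.
- *Test.* Power, PL versus ML with 6 worms each: 0.899 versus 0.899 (latent), 0.841 versus 0.847 (observed). Type I error: 0.050 versus 0.051, and 0.045 versus 0.049. The standard error shrinks along with the estimate.

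**Coverage of the 95% interval.** With b = bias/SE, coverage ≈ Φ(1.96 − b) − Φ(−1.96 − b). At 100 per arm the SE is multiplied by √(51/100) = 0.714.

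- Latent: b = 0.128/0.307 = 0.42, coverage 93%. At 100 per arm b = 0.128/0.219 = 0.58, coverage 91%.
- Observed: b = 0.240/0.338 = 0.71, coverage 89%. At 100 per arm b = 0.240/0.241 = 0.99, coverage 83%.

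Direct simulation gave 92–93% and 89% at 51 per arm, and 88–91% and 81–82% at 100 per arm. ML gave 94–96%.

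**Price of quadrature.** RMSE = √(bias² + SD²).

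- Latent: PL √(0.128² + 0.301²) = 0.327, ML √(0.015² + 0.349²) = 0.349, ratio 1.07.
- Observed: PL √(0.240² + 0.343²) = 0.419, ML √(0.005² + 0.436²) = 0.436, ratio 1.04.

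**The case against.** The strongest reply is that nothing in the stated decision changes. The only rule is a P-value, and it behaves almost identically under both methods. This stands, and it limits the point to estimation.

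Second, the documents never promise an odds ratio or an interval. The endpoint is a percentage, and the person-specific odds ratios of 0.34 and 0.29 depend on the assumed person variance. This stands too. A reader might infer that an odds ratio of 0.37 where 0.29 is true would be a misreported trial result; the documents do not support that, because they commit to no such figure. It does show that the effect measure must be fixed together with the method.

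Third, a reader might infer that percentages from the model would also be pulled toward zero. They would not. For planned values of 30% and 15%, pseudo-likelihood percentages averaged over the person effect came out slightly high: 31.6% and 17.0% (latent), 31.5% and 17.3% (observed). Simply back-transforming the fixed effects gives 28.5% and 13.5%, and 27.0% and 12.2%. The same back-transformation after quadrature gives 25.8% and 10.6%, and 22.8% and 8.2%, which is further from the endpoint because it describes a person with a random effect of zero. Quadrature alone, without a rule for deriving percentages, would therefore not be enough.

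Fourth, leaving a software option to the programmer is common in a protocol-level plan, and the default might not be used. The documents are silent on this, so the bias is conditional.

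**Conclusion.** The point holds as a minor one about estimation. The distribution, link and random effect are specified; the estimation method and the reported effect measure are not. If pseudo-likelihood is used and the ICC is near 0.30, the person-specific log odds ratio is shrunk by about 14% (latent scale) to 20% (observed scale), and the person SD is about 20% too small. The interval for that odds ratio covers about 89–93% at 51 per arm and about 81–91% at 100 per arm. The latter is the case if the upper limit of 300 participants is reached and all have nodule data, so extra enrolment makes coverage worse.

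The figures rest on the default being used, a normal person effect with common variance, and Section 8.1's ICC, which is a planning value on an unstated scale. A reader might infer that the primary test is invalid or the trial underpowered because of this. The calculations do not support that: type I error stays near 5%, and power differs by at most about 1 percentage point.

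**What to change.** Add to Section 8.2, before the nodule results are analysed by arm:

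- The primary and viability models are fitted by maximum likelihood with adaptive quadrature (METHOD=QUAD), or by the Laplace approximation (METHOD=LAPLACE) if a village random effect is added.
- The treatment effect is reported with a 95% confidence interval in two forms: as an odds ratio, labelled person-specific, and as model-based percentages per arm averaged over the person random effect, so that they correspond to the percentage of fertile female worms.

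The cost is one line of code for the method, a short step to average the percentages, and a slightly more variable log odds ratio (RMSE about 4–7% higher at 51 per arm). The sample size and the test are not affected.

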Secondary Objectives:	Safety: 
 1. To compare rates of adverse events grade 3 or higher by treatment group that occur within 7 days of treatment in the subset of participants who have intraocular microfilariae just prior to treatment with IDA 2. To compare rates of ocular adverse events (any grade) by treatment group that occur within 3 months of treatment with IDA Efficacy 
 1. To compare the effect of three treatment regimens for killing adult female O. volvulus worms based on the percentage of all adult female worms in nodules that are alive 18 months after treatment with IDA 2. To compare the effects of three treatment regimens for complete clearance of microfilariae from the skin. 3, 12 and 18 months after treatment with IDA 3. To compare the effects of three treatment regimens for preventing reappearance of microfilariae in the skin at 12, and 18 months after treatment with IDA.
------------------------------	---

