Secondary Objectives:	
Safety:
 
 1. To compare rates of adverse events grade 3 or higher by treatment group that occur within 7 days of treatment in the subset of participants who have intraocular microfilariae just prior to treatment with IDA to those who do not have intraocular microfilariae 2. To compare rates of ocular adverse events (any grade) by treatment group that occur within 3 months of treatment with IDA 
Efficacy
 
 1. To compare the effect of three treatment regimens for killing adult female O. volvulus worms based on the percentage of all adult female worms in nodules that are alive 18 months after treatment. 2. To compare the effects of three treatment regimens for complete clearance of microfilariae from skin snips 3, 12 and 18 months after treatment with IDA. 3. To compare the effects of three treatment regimens for preventing reappearance of microfilariae in the skin at 12, and 18 months after treatment with IDA.

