9.1 Types of Data Collected

Enrollment Data

- Participant identifier
- Informed consent date
- Demographic information (date of birth, gender)
- Pregnancy/breastfeeding status
- Medical history
- Presence of onchocercal nodules
- History of prior MDA treatment
- Physical exam
- Skin exam (including photographs of skin lesions)
- Ocular exam (including retinal and ocular coherence tomography photographs)

Laboratory Results

- Skin snip (including MF count)
- Nodule histology results (number of live/dead female and male worms, etc.)

Participant Monitoring and Follow-up

- Physical exam
- Skin exam (including photographs of skin lesions)
- Ocular exam (including retinal and ocular coherence tomography photographs)

Adverse Event Evaluation

- Adverse event assessment
- Treatment assignment
- Concomitant medication
- Ae description
- Start and stop date
- Outcome
- SAE evaluation and causality to MDA (definite, probable, possible, or unrelated)

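### Section 8.2 analyses viability over all adult worms, but secondary efficacy objective 1 is about adult female worms only

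*Combined protocol and SAP*

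**What the plan says.** Section 4 gives the first secondary efficacy objective as a three-regimen comparison of the "percentage of all adult female worms in nodules that are alive 18 months after treatment". The Protocol Summary (Section 1) has the same objective: "percentage of all adult female worms in nodules that are alive 18 months after treatment with IDA". Hypothesis 1 in Section 3 is also about adult female worms.

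Section 8.2, under the secondary efficacy outcomes, is the only place that says how viability will be analysed: "percentage of all adult worms that are viable will be analyzed using a GLMM". The sentence opens by likening this to the primary analysis, but it does not mention sex.

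Section 9.1 lists the histology data as "number of live/dead female and male worms", so both sexes will be in the dataset.

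Section 8.1 defines the primary outcome per female worm, "100 x fertile female worms/ total female worms", but then states its assumed rates against a different base, for example "30% of the total worms will be fertile females in IVM/ALB group". The 15% and 10% rates for the two IDA arms are worded the same way.

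**The concern.** An objective and its analysis should have the same denominator. Here the objective counts females and the analysis text counts every adult worm. Because male worms are recorded as live or dead, the two percentages can differ, and an analyst following 8.2 to the letter would pool the sexes in a model with no stated sex term.

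Viability is the plan's direct measure of killing, since the primary outcome combines killing with sterilising. Section 4.5 also makes treatment assignment available to the data analysts. With two denominators in one document, the choice between them could be made with the arms known, and pre-specification is meant to prevent that.

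**Working it through.** **1. Is the denominator settled anywhere?**

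| Place | Worms counted for viability |
|---|---|
| Section 1, secondary efficacy objective 1 | adult females |
| Section 4, secondary efficacy objective 1 | adult females |
| Section 8.2, secondary outcomes | all adults |
| Section 8.2, analysis populations | adult worms, sex not stated |
| Section 4.8, nodule reading | live and dead worms distinguished, sex not stated |
| Section 9.1, data collected | both sexes, live and dead |

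Nothing restricts the 8.2 viability analysis to females. The primary outcome in 8.2 is different: its coding is explicitly fertile versus non-fertile female worm.

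**2. What pooling the sexes does to the estimate.** Let m be the male share of worms, taken as the same in both arms, and let dF and dM be the between-arm differences (IVM/ALB minus IDA) in the percentage alive for females and males. Then

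all-worm difference = (1 − m) × dF + m × dM.

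The documents give none of these values. As an illustration, assume females 60% versus 40% alive (dF = 20 points) and males 80% alive in the comparator arm.

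| Assumed male result | m = 20% | m = 1/3 | m = 40% |
|---|---|---|---|
| 80% vs 80% (dM = 0) | 0.8×20 + 0 = 16 | 13.3 | 12 |
| 80% vs 60% (dM = 20) | 16 + 4 = 20 | 20 | 20 |
| 80% vs 40% (dM = 40) | 16 + 8 = 24 | 26.7 | 28 |

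The planned model is on the logit scale, where equal risk differences do not give exactly equal odds ratios. For the middle row at m = 1/3, the all-worm percentages are 66.7% and 46.7%. The odds are 2.00 and 0.875, and the odds ratio is 2.29. For females alone it is 1.50/0.667 = 2.25. (These are simple odds ratios that ignore the person effect.)

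**3. Does the wording in 8.1 affect the sample size?** Inputs from 8.1: rates 30%, 15% and 10%; 6 female worms per person; ICC 0.30; two-sided alpha 0.05; power 80%.

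- Design effect: 1 + 0.30 × (6 − 1) = 2.5.
- Worms per group, pooled-variance formula without continuity correction: n = [1.96 √(2p̄(1−p̄)) + 0.842 √(p₁(1−p₁) + p₂(1−p₂))]² / (p₁−p₂)².
- 30% vs 15%: n = 121 worms; 121 × 2.5 / 6 = 50.4, rounded up to **51** subjects, as stated.
- 30% vs 10%: n = 62 worms; 62 × 2.5 / 6 = 25.8, rounded up to **26** subjects, as stated.

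Both figures reproduce when the rates are applied per female worm.

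**The case against.** The strongest reply is that this is loose drafting. Two objectives say female, and the 8.2 sentence begins by likening itself to the primary analysis, which is per female worm. That is a credible account of how the wording arose. It does not cure the text: the likeness most naturally refers to the mixed model, and the sentence then names its own, wider denominator.

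It is also fair to say that the consequence is limited. One secondary endpoint with no sample size of its own is affected, and a female-only analysis stays possible because the sexes are recorded separately. This bears on how serious the point is, not on whether the two passages agree.

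Two stronger readings are tempting, and the documents do not support either.

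- A reader might infer that including males must dilute the effect. That follows only if males respond less than females. The first row of the illustration assumes no effect on males at all, and the other rows show no change or a larger difference.
- A reader might infer from the total-worms wording that the sample size is wrong. In 8.1 the outcome formula, the cluster size and the 0/1 coding are all per female worm, and 51 and 26 reproduce on that basis. If the rates were shares of both sexes, the female rates would be higher and fewer subjects would be needed. With an assumed 80% female share, for example, 37.5% versus 18.75% needs 90 worms, and 90 × 2.5 / 6 = 37.5, or 38 subjects. The stated 51 would then be conservative.

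**Conclusion.** The mismatch is real and nothing in the documents resolves it: as written, the viability analysis in 8.2 estimates a different quantity from secondary efficacy objective 1. The size and direction of any change in the estimate cannot be fixed from the documents, because male share and male viability are not given. In the illustration, a 20-point female difference becomes anything from 12 to 28 points, assuming 20% to 40% males (the same in both arms) and a male effect of 0 to 40 points.

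The primary fertility analysis is consistently per female worm and is unaffected. The 8.1 wording is an editorial slip with no effect on the stated sample sizes.

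**What to change.** In Section 8.2, replace the all-worm phrase with the objective's own endpoint, the "percentage of all adult female worms in nodules that are alive 18 months after treatment", and state that the mixed model is fitted to female worms only. If male or both-sex viability is of interest, report it as a separately labelled descriptive or supportive analysis.

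In Section 8.1, as an editorial correction, express the 30%, 15% and 10% rates as shares of total female worms. Leave 51 and 26 as they are.

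The cost is wording only: no new data, visits or participants. The change should be made before the nodule data are analysed; Section 8.3 already provides for reporting major changes to the analysis plan, including to the FDA before data lock.

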The clearance of Mf from the posterior chamber of the eye is poorly understood because it is more difficult to visualize this part of the eye. Several studies have shown that anterior segment lesions such as punctate keratitis, sclerosing keratitis, iridocyclitis improved after IVM^{33, 34}, but there are conflicting data about the effectiveness of IVM for improving vision or preventing visual loss related to posterior segment lesions.

The [name] et al. review also discussed the possibility for re-introducing DEC in combination with ivermectin and albendazole, referred to as IDA for treatment of onchocerciasis²⁶. The reason for this is that IDA has been found to be much more efficacious for treatment of lymphatic filariasis (LF)³⁵. This study along with a large multicenter safety study (manuscript development in progress) resulted in the World Health Organization changing its guidelines to recommend IDA for LF outside Africa³⁶. Based on this recommendation Merck Sharp & Dohme Inc agreed to increase

their donation of ivermectin by 100 million doses per year for use of IDA in MDA programs for LF outside of sub-Saharan Africa³⁷. LF is often co-endemic with onchocerciasis in sub-Saharan Africa. This raises the important question of whether IDA can be safely used for LF elimination in coendemic areas. We hypothesize that IDA will be safe for use in persons with onchocerciasis if dermal and ocular Mf are cleared or greatly reduced by pretreatment with ivermectin alone

Many studies have examined Mf clearance from the skin after IVM treatment and these have been summarized in a meta-analysis³⁸. These results show microfilaridermia are reduced by half after 24 h, by 85% after 72 h, by 94% after 1 week, and by 98-99% after 1-2 months. Mf reappear in the skin as early as 3 months post-treatment³⁸.

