Samples will be collected for later studies of biomarkers of *Onchocerca* infection. 5ml of peripheral venous blood and 10 ml of first void morning urine will be obtained prior to the Part II treatment and at 3, 12, and 18 months after treatment. Post-treatment samples will be compared with samples collected prior to the Part I IVM clearing dose and with samples collected just prior to treatment in this study (Part II). Samples will be stored at the UHAS study site until they are shipped to the USA for analysis (see paragraph 6.1). Analysis of samples will take place at the [name] Lab at Washington University in St. Louis. Samples will be stored for up to 35 years and then destroyed according to regulatory guidelines.

Parasitological Evaluations

Palpation for subcutaneous *Onchocerca* nodules: This baseline information will be available from the preceding related study, but nodule palpation will also be performed at the time of nodulectomy

Skin snip testing to detect microfilaria in skin

Skin snip testing for Mf will be performed at 3, 12 and 18 months. We will obtain four (4) skin snips using a corneoscleral punch. Each snip will be weighed on an analytical balance and incubated for at least 8 hours in isotonic saline in a well of a flat-bottomed micro-titre plate at ambient temperature. Microfilariae will be counted by microscopy. Mf number and skin snip weight will be recorded. The mean skin microfilarial density will be calculated and recorded as mf/mg. Skin snips will also be preserved for later PCR testing to detect parasite DNA (more sensitive than microscopy).

Nodulectomies

Nodulectomies will be performed at 18 months after IDA treatment. Nodules will be surgically excised by Ghanaian study medical officers, under local anesthesia (1% xylocaine) in a specially designated room at the University of Health and Allied Sciences School of Public Health Research Centre using aseptic procedures. At the final visit at 18 months post-treatment participants will be brought to the centre in Hohoe for 2 days for nodulectomies. After the procedure they will then be returned to their communities where a study nurse and will be stationed to continue wound management.

Wound treatment for Nodulectomy

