5 POTENTIAL RISKS AND BENEFITS

5.1 Risks of Skin Snips:

This procedure is associated with a small risk of bleeding and infection. The skin will be disinfected before a snip is taken with a sterile scleral punch. The snip (about 2 mg) will cause a superficial wound of the skin at the iliac crests and calves, which will be covered with a plaster for one day. These procedures are routine and designed to minimize risks of infection or bleeding. The scar will be 2 mm or less in size.

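### Section 8.2 compares the arms on skin microfilariae only as zero versus non-zero at 18 months; its one count analysis is a within-person paired t-test that cannot compare the three regimens

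*Combined protocol and SAP*

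**What the plan says.** The Protocol Summary sets a secondary objective of comparing the three regimens on "complete clearance of microfilariae from the skin" at 3, 12 and 18 months. Section 4 words the same objective in terms of skin snips and adds a comparison on reappearance at 12 and 18 months.

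On measurement, section 4.6 states "We will obtain four (4) skin snips using a corneoscleral punch" and "Microfilariae will be counted by microscopy". It also has each snip weighed, records count and weight, and derives a mean density in Mf/mg. Section 5.1 gives the size: "The snip (about 2 mg) will cause a superficial wound of the skin".

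On analysis, section 8.2 has two sentences on skin Mf. The first is "Percent of persons with zero MF at 18 months will be analyzed using a generalized linear model", with a binomial distribution and logit link. The second plans a paired t-test on the pre-to-post change in counts, expressed as percentage reduction and transformed if needed. No detection limit, minimum skin weight or weight adjustment is given.

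**The concern.** The objectives are comparative, so each needs an analysis with treatment arm in it. A paired t-test sets each person's value after treatment against the same person's value before. All three arms receive ivermectin, so such a test can show a fall in every arm and still say nothing about whether IDA does better than IVM/ALB. Finding a significant change in one arm and not in another is not a comparison of the two.

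That leaves zero/non-zero at 18 months as the only specified between-arm skin analysis. It treats one Mf and a hundred Mf alike, and a zero from a light set of snips like a zero from a heavy set. The 3- and 12-month comparisons named in the objectives have no between-arm analysis at all. At stake is whether a real reduction in skin density by IDA would be seen, and whether the count analysis would be chosen only after the data are known.

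**Working it through.** **Plan's own figure.** The documents give no sample size or power for skin Mf. The figure of 51 per group in section 8.1 is for worm fertility, and it reproduces. For 30% versus 15% at two-sided 0.05 and 80% power, n = (1.96 × √(2 × 0.225 × 0.775) + 0.842 × √(0.30 × 0.70 + 0.15 × 0.85))² / 0.15² = 121 worms per arm. Then 121 × [1 + 0.30 × (6 − 1)] / 6 = 121 × 2.5 / 6 = 50.4, so 51. I use 51 per arm below as a convenient size; up to 300 may be enrolled.

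**Skin read.** 4 snips × about 2 mg = about 8 mg per visit.

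**What a zero means.** With Poisson counts, P(zero) = exp(−weight × density). Detection in 8 mg is therefore 1 − exp(−8d):

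| Density (Mf/mg) | Detected |
|---|---|
| 0.05 | 33% |
| 0.1 | 55% |
| 0.2 | 80% |
| 0.375 | 95% |
| 0.5 | 98% |

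Weight matters at low density. At 0.1 Mf/mg, P(zero) is exp(−0.6) = 55% if 6 mg is read and exp(−1.0) = 37% if 10 mg is read (6 and 10 mg are illustrative).

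**Power, when IDA lowers density.** Assumptions: 51 per arm, 8 mg read, densities varying between persons as a gamma with shape k. Then P(zero) = (1 + 8m/k)^(−k) for mean density m. Hand check for 0.5 versus 0.25 Mf/mg, k = 1:
- P(zero) is 1/5 = 20.0% versus 1/3 = 33.3%, pooled 26.7%.
- Standard error = √(2 × 0.267 × 0.733 / 51) = 0.0876.
- z = 0.133 / 0.0876 = 1.52, so power = Φ(1.52 − 1.96) = 33%.

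Simulated power, two-sided 0.05:

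| Control vs IDA mean (Mf/mg), k | Zero/non-zero | Mann-Whitney on counts | t-test on log density |
|---|---|---|---|
| 0.05 vs 0.025, k = 1 | 30% | 30% | 35% |
| 0.1 vs 0.05, k = 1 | 38% | 45% | 50% |
| 0.5 vs 0.25, k = 1 | 33% | 73% | 76% |
| 0.5 vs 0.25, k = 0.3 | 17% | 24% | 32% |
| 1 vs 0.5, k = 1 | 21% | not run | 74% |
| 1 vs 0.33, k = 0.3 | 29% | not run | 62% |
| 2 vs 1, k = 1 | 14% | 85% | 82% |

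Over 18 scenarios with control means of 0.5-3 Mf/mg, two- or three-fold reduction and k of 0.3-1, zero/non-zero had 11-72% power and the log-density test 28-99%. The log-density test was higher in all 18.

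**Power, when IDA raises the share truly clear.** Assume 20% versus 50% truly clear, equal density in the rest, k = 1:

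| Mean in the uncleared (Mf/mg) | Zero/non-zero | Mann-Whitney on counts |
|---|---|---|
| 0.1 | 29% | 27% |
| 0.5 | 72% | 61% |
| 2 | 86% | 69% |

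A negative binomial model does much worse here: 26% against 80% for zero/non-zero at 1 Mf/mg.

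**Type I error.** Under the null (0.5 Mf/mg in both arms, k = 0.3), rejection was 6.1% for zero/non-zero, 5.8% for Mann-Whitney, 5.7% for the log-density test and 8.6% for the negative binomial likelihood-ratio test. I therefore do not rely on negative binomial power for the gain.

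**The case against.** The strongest defence is that zero/non-zero is the right analysis for a clearance objective. The hypothesis is that IDA kills or sterilizes adult worms, and if that makes more people truly clear, the binary analysis has more power than counts. That stands, and it is why counts should not displace it. The endpoint is also secondary, the trial is powered on worm fertility, and the same four-snip reading in every arm keeps the randomized comparison valid.

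A second defence is that the percentage reduction could be computed per person and then compared across arms. That would answer the concern, but section 8.2 names a paired test and no arm comparison.

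Two stronger readings are tempting, and the documents do not support them.

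- A reader might infer that the snips cannot see the densities expected, so most zeros are false. Starting from the entry floor of 3 Mf/mg, a fall "by 98-99% after 1-2 months" leaves 0.03-0.06 Mf/mg, at which 62-79% of infected people would read zero. But 3 Mf/mg is a floor and no mean is given; from an assumed 20 Mf/mg the figure is 4-20%. The fall is documented at 1-2 months, with Mf reappearing from 3 months, while the planned analysis is at 18 months. The point bears more on the 3-month visit.
- A reader might infer that the plan throws the counts away. It does not: it records counts and weights, derives Mf/mg and analyses percentage reduction. The gap is that this analysis does not compare arms.

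**Conclusion.** The gap is real and moderate. As written, the only between-arm skin-Mf analysis is zero/non-zero at 18 months, unadjusted for skin weight, and the count analysis cannot answer a comparative objective.

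If IDA lowers density two- to three-fold from an assumed 18-month control mean of 0.5-1 Mf/mg, a count analysis with controlled type I error raises power from about 20-33% to about 60-76% in three of the scenarios checked. With a mere halving and wide spread (k = 0.3) the gain is smaller, 17% to 32% at 0.5 Mf/mg. Near 0.05 Mf/mg there is little gain, and if IDA mainly raises the share truly clear the count analysis loses.

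It might be inferred that a density ratio should become the main skin result; these figures do not support that. The two analyses are sensitive to different effects, and both should be reported. The 18-month densities, the between-person spread and the 51 per arm are assumptions, so the power figures show direction and rough size only.

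**What to change.** In section 8.2:

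1. Keep the zero-Mf percentage as the analysis of the clearance objective. Describe it as *no Mf detected in four snips (about 8 mg)* and report the total skin weight read.
2. Replace the paired t-test with a between-arm comparison of Mf counts at each skin-snip visit (3, 12 and 18 months). One option is a negative binomial model of the total count with log(total snip weight) as offset and its type I error checked by permutation; another is a test on log density. Report the density ratio of each IDA arm versus IVM/ALB.
3. State that the count result is shown beside the zero-Mf result and does not replace it.

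The cost is SAP wording, since counts and weights are already recorded under section 4.6. Section 8.3 provides a route for reporting major SAP changes, including to the FDA before data lock. The small downside is one more secondary result to report and interpret, and the two may differ.
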